### C.5 Study Design

The Endurant Evo US Clinical Trial is prospective, multi-center, pre-market, non-randomized, single-arm trial. The trial is designed to assess the clinical safety and performance of the Endurant Evo AAA Stent graft system.

Globally, a total of 140 subjects will be concurrently enrolled in the United States and outside the United States to support the primary endpoint. Up to 50% of subject data used to support PMA approval may come from subjects enrolled at sites outside of the US under a separate CE Mark study protocol; the Endurant Evo International Clinical Trial protocol. The Endurant Evo International Clinical Trial protocol and Endurant Evo US Clinical Trial protocol will be identical with respect to the inclusion/exclusion criteria, and follow up data collection.

Given the UADEs that have occurred within the Endurant Evo study (transition stent fracture, partial suprarenal stent detachment, and suprarenal stent fracture), enrollment was terminated. Total global enrollment, upon termination, was 139 subjects. This includes 70 subjects enrolled in the United States and 69 enrolled outside the United States.

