### H.1 Analysis of Clinical Data

All observations will be analyzed descriptively. In general, qualitative parameters will be described by their distribution frequencies; quantitative parameters will be described by their mean, standard deviation, minimum, maximum, median, and number of subjects with assessable data.

The survival from all-cause mortality over one year time or longer will be described by the Kaplan-Meier survival curve and the associated Kaplan-Meier estimate will be calculated along with its standard error using the Greenwood method.

For events such as AEs, deaths and secondary procedures, that can occur or are observed at any time during the study, no time window will be applied. For such events, an event that occurs "within 1 month or 30 days" is an event that takes place between Days 0 to 30, inclusive. Similarly, an event that occurs "within 12 months or 365 days" is an event occurring between Day 0 to Day 365, inclusive. Date of event onset will be used to determine when the event occurred. Day 0 is referring to the day of index procedure.

For image-based assessments, such as stent-graft endoleak, patency, and other observations, the following time windows will be applied for by-visit data summaries:

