#### *Secondary Endpoints*

The following secondary endpoints will be evaluated:

- All-cause mortality within 30, 183, and 365 days
- Aneurysm-related mortality within 30, 183, and 365 days
- Secondary procedures to correct Type I and III endoleaks within 183 and 365 days
- Secondary procedures within 183 and 365 days
- Serious adverse events within 30, 183, and 365 days
- Conversion to open surgery within 183 and 365 days
- Aneurysm ruptures within 183 and 365 days
- Major adverse events within 183 and 365 days
- Stent graft migration at 6- and 12-month follow-up visits (as compared to 1-month imaging)
- Aneurysm expansion >5 mm at 6- and 12-month follow-up visits (as compared to 1-month imaging)
- All endoleaks based on imaging findings at 1-, 6-, and 12-month follow-up visits
- Stent graft occlusions based on imaging findings through 1-, 6- and 12 months
- Device deficiencies based on imaging findings through 6 and 12 months.

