## 8.5. Analysis of the Secondary Endpoints

Descriptive statistical analyses will be performed on secondary endpoints. No inferential statistical analysis is planned for secondary endpoints.

Event rates such as mortality, secondary procedures, serious adverse events, conversion to open surgery, and aneurysm ruptures will be calculated in the same way as the MAE rate, specified in Table 3.

The survival from all-cause and aneurysm-related mortality over one year time or longer will be presented with the Kaplan-Meier survival curve and the associated Kaplan-Meier estimate will be calculated along with its standard error using the Greenwood method.

Imaging based event rate such as stent graft migration, aneurysm expansion, endoleaks, stent graft occlusions, and device deficiencies will be calculated in the way as specified in Table 4.

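### If no aneurysm-related deaths occur, SAP 8.5 gives a standard error of exactly zero and no interval to show the uncertainty that remains

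*SAP*

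**What the plan says.** SAP 8.5 sets the scope as "The survival from all-cause and aneurysm-related mortality over one year time or longer". For both outcomes it plans a Kaplan-Meier curve, and "the associated Kaplan-Meier estimate will be calculated along with its standard error using the Greenwood method". The protocol is narrower. Section H.1 reads "The survival from all-cause mortality over one year time or longer will be described by the Kaplan-Meier survival curve" and does not extend the method to aneurysm-related death.

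The SAP lists the endpoint in section 5 as "Aneurysm-related mortality within 30, 183, and 365 days". Section 8.5 adds "No inferential statistical analysis is planned for secondary endpoints". It also has "Event rates such as mortality, secondary procedures, serious adverse events, conversion to open surgery, and aneurysm ruptures" calculated as the crude proportion m/(m + k) of SAP Table 3. Neither the Kaplan-Meier estimate nor the crude proportion is given a confidence interval. Neither document states an expected number of aneurysm-related deaths.

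On cohort size, Protocol C.5 states "Total global enrollment, upon termination, was 139 subjects" and "This includes 70 subjects enrolled in the United States and 69 enrolled outside the United States".

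**The concern.** A standard error is the only measure of precision that the SAP attaches to this outcome. Greenwood's formula draws its variance from the observed events, so with no events it has nothing to draw on. The report would then show 100% freedom from aneurysm-related death with a standard error of 0. Read literally, that is perfect precision from a cohort of 139, or of 70 if the US trial is reported alone.

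The upper end of the plausible range matters here. Protocol C.5 records that enrolment was stopped because of stent fractures and a partial stent detachment. Protocol J.3 says the observed risks occur at higher rates than with devices already on the market. Follow-up runs to five years. A reader of the final report will want to know how large the risk of aneurysm-related death could still be, and the planned output does not say when the count is zero.

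**Working it through.** The plan gives no figure for this endpoint or its standard error, so there is none to reproduce.

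**Inputs.** N = 139 globally and 70 in the US (Protocol C.5). Standard error by Greenwood (SAP 8.5). The true risks and event counts below are assumptions. There is no censoring unless stated.

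**Formula.** Greenwood's SE = S × √[Σ d/(n(n − d))], summed over event times. Without censoring, and with d deaths in n subjects, it equals √[p(1 − p)/n], where p = d/n.

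**No events.** The sum has no terms, so SE = 0 for any n, with or without censoring.

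**How likely is that?** The probability of no deaths is (1 − risk)^N.

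| Assumed true risk | N = 139 | N = 70 |
|---|---|---|
| 0.5% | 50% | 70% |
| 1% | 25% | 49% |
| 2% | 6% | 24% |

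**What is zero compatible with?** The exact two-sided 95% upper limit is 1 − 0.025^(1/n):
- n = 139: 2.62%
- n = 119, the planned evaluable number, used only to illustrate a smaller denominator: 3.05%
- n = 70: 5.13%

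**One or two events, N = 139.**
- One death: p = 1/139 = 0.72%; SE = (138/139) × √[1/(139 × 138)] = 0.72%.
- Two deaths: p = 2/139 = 1.44%; SE = (137/139) × √[2/(139 × 137)] = 1.01%.

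The binomial sampling standard deviation at true rates of 0.72% and 1.44% is also 0.72% and 1.01%. Without censoring the two formulas are the same, so the match is expected. The SE is as large as the estimate with one death and about 70% of it with two (1.01/1.44). Censoring raises it: one death with an assumed 60 at risk gives 1.67% with SE 1.65%.

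**What a reader would get from estimate ± 1.96 SE.** The SAP does not plan this interval.

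| Deaths of 139 | Symmetric limits | Exact (Clopper-Pearson) limits | Log-log Greenwood limits |
|---|---|---|---|
| 0 | 0 to 0 | 0 to 2.62% | cannot be formed |
| 1 | −0.69% to 2.12% | 0.02% to 3.94% | 0.10% to 5.00% |
| 2 | −0.54% to 3.42% | 0.17% to 5.10% | 0.36% to 5.63% |

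**Where the symmetric interval loses coverage.** At true risks of 0.5%, 1% and 1.5% with N = 139, its coverage is 50.1%, 75.2% and 87.6%. The probability of at least one death is 50.2%, 75.3% and 87.8%. Nearly all of the shortfall is therefore the zero-event case.

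**The case against.** The strongest reply is that the SAP makes no inferential claim here. It plans an estimate and a standard error for a descriptive endpoint, and no test or success criterion uses them. Study success rests on the two primary tests, which already use an exact binomial method (SAP 8.4). The crude proportion from Table 3 will show zero over a stated denominator, and a statistician can derive an exact bound from that. Counts also need not be very low: Protocol L.2 presumes a death within 30 days of any procedure to treat the aneurysm, including a secondary one, to be aneurysm-related unless evidence shows otherwise.

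Most of this stands, and it limits the point to a minor one. It does not remove it. Having chosen to report a measure of precision, the SAP should not use one that reads zero in a plausible case. The crude proportion has no interval either, so the reader is left to do the calculation.

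A reader might go further and infer that Greenwood's standard error is far too small with one or two deaths and should be dropped for sparse outcomes. The numbers do not support that. The standard error then matches the binomial sampling variation, and on the log-log scale it gives upper limits above the exact ones. The understated limits come from a symmetric interval that the SAP never specifies.

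**Conclusion.** The point holds in a narrow form. If no aneurysm-related deaths are observed, SAP 8.5 produces a standard error of exactly zero with no interval beside it, although the data would be compatible with a risk of up to 2.6% (0 of 139) or 5.1% (0 of 70). These limits assume no censoring; fewer subjects at risk would raise them. How likely a zero count is depends on the true risk, which the documents do not give: about 50% to 6% at N = 139 over assumed risks of 0.5% to 2%.

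Three broader readings are not supported:
- The documents do not rank aneurysm-related mortality as the most serious device outcome.
- The planned output is not false certainty in general; the defect is confined to the zero-event case.
- Protocol H.1 does not share the defect, because it applies the method to all-cause mortality only.

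The consequence is an uninformative error bar on a descriptive secondary endpoint. Study success is unaffected.

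**What to change.** In SAP 8.5, keep the Kaplan-Meier curve and the Greenwood standard error. Add one sentence: for aneurysm-related mortality, each reported time point also carries 95% limits valid for sparse events, by Clopper-Pearson or the beta-product method. When no events have occurred, an exact upper bound based on the number at risk is given. Name one method in advance so that the choice does not follow the data. Asking only for log-log limits would not close the gap, because they cannot be formed with zero events.

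The cost is a sentence in the SAP, a few lines of code, slightly more output and an upper limit that looks less favourable than a bare 0%. No new data are needed, no primary analysis changes, and Protocol H.1 can stay as it is.

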## 9. Additional Data Summaries / Supplemental Analyses

Descriptive data summaries will be provided for acute procedural observations and clinical utility measures.

## 10. Data Screening and Acceptance

Data management will be done according to Medtronic SOPs and the Data Management Plan for this clinical study. These documents will be made available upon request.

All collected data will be reviewed for completeness, correctness and consistency. In case of issues, queries will be sent to the investigator or designee to complete, correct or comment the data.

## 11. List of Planned Tables, Listings, and Figures

List of planned tables, listing, and figures for the analyses can be found in Appendix.

## 12. Appendices

### 12.1. Imaging Technique and Sensitivity

Anatomy/Stent Graft Issue Detected	CT with contrast	CT without contrast	MRA	MRI	Abdominal X-ray	Duplex CDUS (Ultrasound)	Angiogram, Aortogram and Arteriogram
AAA Diameter and Length	1	2	1	2	4	3	3
Stent graft migration	1	2	1	2	3	4	2-3
Stent graft fracture	2	3	2	3	1	4	2-3
Stent graft kinking	2	3	2	3	1	4	2-3
Stent graft twisting	2	3	2	3	1	4	2-3
Stent graft patency	1	4	1	4	4	2	2-3
Endoleaks	1	4	1	4	4	2	2-3
Occlusion	1	4	1	4	4	2	2-3
Stenosis	1	4	1	4	4	2-3	2-3
Stent Graft Fabric Defect	1	4	1	4	4	4	2-3
1 = Highly visible		2 = visible		3 = Not very visible (potential artifacts)		4 = Invisible	

### 12.2. Table, listing, and figure templates/shells

A separate attachment includes a list of planned tables, listings and figures.
